## 10.2. The Number of Participants

There is no data to allow sample size calculation, nor are there data on recruitment and loss of patients. We estimate that it should be possible to recruit a total of 400 patients, which should be sufficient to detect any worthwhile benefit.

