## 3. BACKGROUND AND RATIONALE

#### **Background**

Patients consistently complain of lack of sleep due to noises throughout the night from: patients, staff, machines and buzzers as well as complaining about bright lights being left on, monitors left active and LEDs flashing throughout the night. This has a severe negative impact on a patient's hospital experience, and has been associated with increased risk of acute confusion, increased medication usage with their side-effects, delayed hospital discharge (at a cost of £273 per day) and worse health outcomes. In this project we aim to investigate whether the simple solution of earplugs and an eye mask can improve the inpatient experience through enhancing sleep.

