# 5. STUDY DESIGN

#### Randomised controlled trial

Pilot data collection 2 weeks from approval of study. 3 months data proper once pilot data has been reviewed and any required changes noted. Data collected from adult inpatients on 10 inpatient wards. Pilot data collection is to identify any problems with the data collection that may arise. If no changes to the protocol are made then this pilot data will be incorporated with the data proper.

Targeted recruitment population: 400 patients total including up to 20 from pilot data. Patients randomised to either intervention (earplugs and eye masks) or control (routine care).

Intervention will be allocated via pre-performed simple randomisation concealed in opaque envelopes with intervention and non-intervention envelopes indistinguishable from one another which will be distributed in batches to each ward engaged in the study.

SleepSure sleep questionnaire will be given to all patients >1 day after recruitment.

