# **10.1.** Description of Statistical Methods

There will be no interim analysis.

The primary analyses will be to compare the two groups on all items collected, using t-test and Mann-Whitney U tests as appropriate with two-tailed testing (i.e. accepting that harm is also possible). The expectation is that the intervention group will have:

- Better sleep on the questionnaire
- Less use of night sedation over their hospital stay
- Less falls over their hospital stay
- A shorter length of stay

Secondary analyses will investigate:

- Variation between wards on all measures, irrespective of patient group.
- Reported use of and problems with the earplugs and eye masks.

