### 10.3. Analysis of Outcome Measures

All participant data will be used excluding those that withdrew consent or did not complete the study questionnaire.

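### Section 10.2 claims 400 patients suffice for any worthwhile benefit: this is uncalculated, fails for falls, is unsupported for length of stay, and is not limited to the sleep score

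*Combined protocol and SAP*

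**What the plan says.** Section 5 sets the size: "Targeted recruitment population: 400 patients total including up to 20 from pilot data". Section 10.2 explains where it comes from. It states "There is no data to allow sample size calculation", adds "nor are there data on recruitment and loss of patients", gives 400 as the number that can probably be recruited, and concludes that this is a total "which should be sufficient to detect any worthwhile benefit". No outcome, difference, power or significance level is attached to that conclusion.

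Section 10.1 describes the primary analyses as between-group comparisons of every item collected, by t-test or Mann-Whitney U test, two-tailed. Its expected benefits include better sleep, less night sedation, a shorter stay and "Less falls over their hospital stay". The synopsis, section 3 (The question) and section 4 differ: there, sleep is the only primary question, and length of stay, falls and sleep medication are secondary.

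Section 10.3 analyses all participants "excluding those that withdrew consent or did not complete the study questionnaire".

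**The concern.** A statement about what a trial can detect needs some calculation behind it, and section 10.2 says there was none. Because the statement names no outcome, and section 10.1 puts every comparison at primary level, a reader can fairly apply it to falls, sedation and length of stay as well as sleep.

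The stake is how a non-significant result is read. The plan specifies hypothesis tests, mentions no confidence intervals, and does not say how a null result on these outcomes will be interpreted. Set beside a protocol that asserts sufficiency, such a result could be taken as evidence against benefit when the trial had little chance of finding one.

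**Working it through.** **Inputs from the plan.** Total 400 (sections 5 and 10.2); equal chance of each arm by simple randomisation (7.4), so about 200 per arm; two-tailed t-test or Mann-Whitney (10.1).

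**Assumptions, because the plan is silent.** Significance level 5%; control risk of any fall 2% to 10%; length-of-stay SD 3 to 10 days; 300 analysed as an example of loss. Falls are treated as any fall, yes or no.

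**The plan's own figure.** The 400 cannot be reproduced, since no effect size, SD, event rate, power or significance level is given.

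**Sleep score.** In SD units the detectable difference needs no prior data: d = (z₀.₉₇₅ + z_power) × √(2/n).
- n = 200, 80% power: (1.960 + 0.842) × √(2/200) = 0.280; with the t distribution, 0.281.
- n = 200, 90% power: (1.960 + 1.282) × 0.100 = 0.324; with t, 0.325.
- n = 150: with t, about 0.325 (80%) and 0.376 (90%).

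**Falls.** Approximate power for a halving is Φ(Δ/SE − 1.96), with SE = √{[p₁(1−p₁) + p₂(1−p₂)]/n}. For 5% against 2.5%: SE = √{(0.0475 + 0.024375)/200} = 0.01896; 0.025/0.01896 = 1.319; Φ(1.319 − 1.960) = 26%. Exact enumeration of the possible counts gives the last two columns.

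| Control risk | Expected fallers, control v intervention | Approximation | t-test | Fisher's exact test |
|---|---|---|---|---|
| 2% | 4 v 2 | 13% | 12% | 4% |
| 3% | 6 v 3 | 17% | 16% | 9% |
| 5% | 10 v 5 | 26% | 26% | 18% |
| 10% | 20 v 10 | 48% | 47% | 41% |

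At 1% the approximation gives 8%. For 80% power to detect a halving, the total needed is 4638, 3068, 1812 and 870 at 2%, 3%, 5% and 10%.

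**Length of stay.** Power ≈ Φ(Δ/(SD × √(2/200)) − 1.96). For 1 day at SD 5: 1/(5 × 0.1) = 2.0, and Φ(0.04) is about 52%; with t, 51%. All t-test results:

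| SD (days) | 0.5 day | 1 day | 2 days |
|---|---|---|---|
| 3 | 38% | 91% | 100% |
| 5 | 17% | 51% | 98% |
| 7 | 11% | 30% | 81% |
| 10 | 8% | 17% | 51% |

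Stay is usually skewed, so Mann-Whitney was simulated on rounded lognormal stays (assumed median 4 days). Power for a 20% reduction was 77% and 56% at log-scale SDs of 0.8 and 1.0; for a 10% reduction it was 25% and 17%.

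**Loss.** Section 10.3 removes non-completers from every analysis, including falls and stay, which come from routine records. At 150 per arm, power for 5% against 2.5% drops from 26% to about 20% (Fisher: from 18% to 12%).

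**Sedation.** The plan gives no figure for zopiclone use, and no power was computed.

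**The case against.** The best defence is that sleep is the primary question in sections 1, 3 and 4, that trials need not be powered for secondary outcomes, and that section 10.2 openly admits there were no data. For the sleep score, about 0.28 SD is a reasonable sensitivity. All of that stands. Low power for a secondary outcome is no fault in itself. The fault is a sentence that sets no limit, together with section 10.1 making every comparison primary.

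Three stronger readings are tempting and should be resisted.

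- *That the trial cannot detect a worthwhile effect on length of stay.* The documents give no SD and define no worthwhile difference. Section 3 values delayed discharge "at a cost of £273 per day", so half a day is 0.5 × £273 = £136.50, but that is background. The plan sets no half-day threshold and gives no cost for the pack. A 1-day effect is well covered at SD 3, and a 2-day effect up to SD 7.
- *That the trial would miss even complete prevention of falls.* Fisher's exact test gives 21%, 56% and 94% power at 2%, 3% and 5%, but section 10.1 does not name that test. The t-test gives 57%, 85% and 99%.
- *That null results will be misreported.* This is a prediction. The plan leaves their interpretation open and says nothing more.

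**Conclusion.** The adequacy sentence has no calculation behind it and is wrong as written, because it covers falls. Power to detect a halving stays below 50% at every assumed control risk from 1% to 10%, by either test, and a halving would be worthwhile on any ordinary view. For length of stay the claim is unsupported: power for half a day is 8% to 38% across SDs of 10 to 3 days, while larger effects may or may not be detectable depending on an SD that the plan does not give. These results assume a two-sided 5% level and 200 analysed per arm; the exclusion in section 10.3 lowers them. The sample size for the primary question is not in dispute, and the case for changing the text rests on the unqualified wording and on section 10.1's conflict with sections 1, 3 and 4.

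**What to change.** Keep 400 and change the wording.

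1. In section 10.2, replace the sufficiency sentence with the detectable difference for the sleep score at a two-sided 5% level: 0.281 SD (80% power) and 0.325 SD (90%) with 400 analysed, and about 0.325 and 0.376 SD if, as a stated assumption, 300 are analysed.
2. In section 10.1, name the sleep score as the only primary analysis, in line with sections 1, 3 and 4, and list falls, length of stay and sedation as secondary.
3. State that the trial is not powered for those three outcomes. Report them as estimates with 95% confidence intervals, and say that a non-significant result will not be taken as evidence of no benefit.

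The cost is protocol text only, with no extra patients. The downside is that the stated capability looks less favourable.

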### 10.3. Analysis of Outcome Measures

All participant data will be used excluding those that withdrew consent or did not complete the study questionnaire.

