### 1. SYNOPSIS

Study Title	SleepSure: a randomised controlled trial to assess the effects of eye masks and earplugs on the quality of sleep for patients in hospital.			
Internal ref. no. / short title	SleepSure: a study aimed at improving sleep for hospital inpatients			
Study Design	Randomised Controlled Trial			
Study Participants	Patients admitted to adult general medical and surgical wards at Oxford University Hospitals NHS Foundation Trust			
Planned Sample Size	400			
Planned Study Period	01 February 2016- 31 January 2017 Pilot data collection 01 February 2016 to 14 February 2015 Recruitment 01 March 2016 – 31 May 2016 (last follow-up 14 June 2016)			
	Objectives	Outcome Measures		
Primary	Do earplugs and eye masks help hospital patients to sleep better?	SleepSure Questionnaire, based on the validated Richards-Campbell Sleep Questionnaire		
Secondary	Does the use of earplugs and eye masks lead to a reduced length of stay, reduced incidence of falls or reduced use of sleep aid medication? How many patients provided with earplugs and an eye mask choose to use them?	Length of stay (days) Number of falls recorded during stay Doses of zopiclone (sleeping tablet) used to help sleep during stay Use of earplugs and eye masks (SleepSure sleep questionnaire)		

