### 6.2 Inclusion criteria:

Eligible candidates at the point of enrolment must:

- Be 18 years of age
- Be expected to stay in Oxford University Hospitals NHS Foundation Trust for at least one more night
- Be able to understand and use earplugs and eye mask.
- Have basic understanding of English reading and writing.
- Be considered likely to have the Mental Capacity to give consent for use of personal data in the study at the point of filling in the SleepSure Questionnaire (>1 day after recruitment). NB/ Data will not be collected from individuals who are unable to give consent with the filling in of the SleepSure questionnaire.
- Be expected to be able to fill in the SleepSure Questionnaire with or without assistance

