# 7.2. Informed Consent

Each patient considered eligible will be given a patient information sheet by a nurse on the ward, part of the direct care team. Following this they will be approached by the SleepSure research nurse who will give them a short verbal explanation that will cover:

- The goal of the study (i.e. to study how to improve sleep)
- The trial intervention (i.e. aircraft style earplugs and eye mask)
- The fact that only a 50% chance of getting intervention (random allocation)
- The collection of data (one questionnaire) >1 day after recruitment
- The collection and use of some routine hospital data (falls, use of sleeping tablets, length of stay)
- The option to withdraw consent at any time
- The specific action of having being presented with a SleepSure Questionnaire >1 day after recruitment, which if not filled in will be taken as a refusal of consent for the use of that data in the trial.

A written consent form will be used.

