# 7.4. Randomisation, blinding and code-breaking

Every patient recruited will first be registered by the SleepSure research nurse onto an electronic password-protected Participant ID log in a secure location on the Trust network. This will generate a trial number (e.g. WPH WdA 007 [hospital, ward, number]).

Randomisation:

Using a random number generator performing simple randomisation opaque numbered envelopes will be filled with a piece of paper stating control or intervention with an equal chance of each individual envelope containing a control or an intervention instruction. 50 sealed envelopes will be stacked into a box on each ward, each with a unique identifier number on the outside. When a potential participant is identified the SleepSure research nurse will go to the next envelope in the box and open it to determine if the patient is in the control or intervention arm.

If the patient is allocated to the trial arm, the research nurse will give the patient a set of earplugs and an eyeshade, and explain their use, checking that the patient can use and remove them safely giving instruction as required. The earplugs and eye mask will then be placed into a transparent plastic wallet, labelled with the patient's name, the study and placed within easy reach of the patient.

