### 13.6. Expenses and Benefits

No expenses will be paid (none will arise), but patients in the intervention group may keep the equipment if they wish.

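### The primary sleep comparison uses only patients who completed the questionnaire after an open allocation, with no planned comparison of return by arm and no sensitivity analysis

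*Combined protocol and SAP*

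**What the plan says.** The analysis set is defined in section 10.3: "All participant data will be used excluding those that withdrew consent or did not complete the study questionnaire". Sections 1 and 4 make the SleepSure questionnaire the primary outcome.

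On timing, section 5 states: "SleepSure sleep questionnaire will be given to all patients >1 day after recruitment". By then the arm is known. Under section 7.4, for a patient allocated to the aids, "the research nurse will give the patient a set of earplugs and an eyeshade, and explain their use". Section 13.6 adds that "patients in the intervention group may keep the equipment if they wish", and section 13.7 decides to give controls nothing. Section 7.4 has blinding in its title but describes none.

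On non-return, section 7.2 tells patients that they will be presented with a questionnaire, "which if not filled in will be taken as a refusal of consent for the use of that data in the trial". Section 6.2 adds: "Data will not be collected from individuals who are unable to give consent with the filling in of the SleepSure questionnaire". Early discharge is another route, because the entry criterion is only "Be expected to stay in Oxford University Hospitals NHS Foundation Trust for at least one more night".

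Section 7.5 takes no baseline sleep measure. Section 7.7 records the reason for any withdrawal, and any death during the admission. Section 7.8 gives a questionnaire to patients still in hospital when follow-up closes. None of these is linked to an analysis by arm. Section 10 has no missing-data method.

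**The concern.** A complete-case difference in mean sleep score is unbiased when non-return is unrelated to sleep within each arm, or when any such relation has the same net effect in both arms. Neither can be taken for granted here. The outcome is self-reported, patients know their arm, one arm has been given something and the other has not, and leaving the form blank is itself the way to refuse. Section 13.7 already recognises that expectation may differ between arms. The same knowledge could affect who responds.

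Without a baseline sleep score, missing values cannot be predicted from earlier sleep. As planned, a false difference, or a true difference that is masked, would come out of the t-test or Mann-Whitney test with nothing in the report to reveal it.

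This point is about the sleep score, for which the questionnaire is the only source.

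**Working it through.** **Inputs from the plan.** 400 patients (section 10.2); equal chance of each arm (section 7.4), taken as 200 per arm; two-tailed testing (section 10.1). Section 10.2 says there are no data for a sample size calculation or on loss, so the plan has no figure of its own to reproduce.

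**Assumptions.** Significance level 5%, which the plan does not state. No true effect. Scores in SD units, with the same SD in both arms. Return rates of 65% to 90%. A gap of 0.5 SD between returners and non-returners, in one or both arms.

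**Formulas.** Let m be the fraction not returning the form and g the returner mean minus the non-returner mean, with higher scores meaning better sleep; I is intervention and C is control.

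- Bias = m_I × g_I − m_C × g_C. Positive favours the intervention.
- SE = √(1/n_I + 1/n_C), with n = 200 × (1 − m) in each arm.
- Rejection rate = Φ(bias/SE − 1.96) + Φ(−bias/SE − 1.96). The first term is false benefit, the second false harm.

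**80% return with the aids, 70% in controls.** n_I = 160, n_C = 140, SE = √(1/160 + 1/140) = 0.116.

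| 0.5 SD gap in | Bias (SD) | False benefit | False harm | Total |
|---|---|---|---|---|
| both arms | 0.20 × 0.5 − 0.30 × 0.5 = −0.05 | 0.8% | 6.3% | 7% |
| controls only | 0 − 0.30 × 0.5 = −0.15 | 0.06% | 25.3% | 25% |
| intervention only | 0.20 × 0.5 − 0 = +0.10 | 13.7% | 0.2% | 14% |

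**Other return rates, gap in controls only.**

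- 90% and 80%: bias −0.20 × 0.5 = −0.10 SD; n = 180 and 160; rejection 15%.
- 75% and 65%: bias −0.35 × 0.5 = −0.175 SD; n = 150 and 130; rejection 31%.

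**Equal return, 80% in both arms** (n = 160 and 160).

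- Same gap in both arms: 0.20 × 0.5 − 0.20 × 0.5 = 0; rejection 5%.
- Gap in controls only: −0.20 × 0.5 = −0.10 SD; rejection 14.5%.

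Unequal return is therefore not required for bias. Unequal return also does no harm if non-return is unrelated to sleep (g = 0 in both arms). What matters is whether the product m × g differs between arms.

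**The case against.** The other side has a fair case. Every return rate and gap above is assumed. Nothing in the documents supports a gap confined to one arm, and with the same gap in both arms the rejection rate is 7%, close to nominal. Return may be good: a research nurse hands over a single form (section 7.6) and section 6.2 allows help in filling it in. Section 7.7 records reasons for withdrawal, and the participant ID log and numbered envelopes would let non-return be counted by arm. All of this stands. It limits what can be said about size, but being able to count non-return is not a plan to report it or to test the result against it.

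Some stronger readings are tempting, and the documents do not support them:

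- *Any blank item excludes the patient, so controls who skip the aid-use questions are lost.* Section 10.3 speaks of not completing the questionnaire and section 7.2 of not filling it in. Neither defines a partly filled form. The questionnaire is not reproduced, so its items and routing are unknown. The ambiguity is worth closing, but no loss can be computed from it.
- *Non-return is always the patient's choice.* Discharge, lost capacity, death and withdrawal by the investigator are also routes.
- *The raised rejection rate means false claims of benefit.* With more controls missing and non-returners sleeping worse in controls only, or in both arms, the error is almost wholly or mainly false harm. It turns to false benefit when the gap lies in the intervention arm.

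**Conclusion.** The point holds as a gap in the analysis plan. The primary comparison is restricted by an event that follows an open allocation, and no planned analysis would show whether that restriction drives the result. Under the stated assumptions the bias runs from 0.175 SD against the intervention to 0.10 SD in its favour, with two-sided rejection rates from 5% (equal return, same gap) to 31%. These are illustrations of sensitivity. They do not predict this trial's error rate: the documents fix neither the direction nor the size of the bias.

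**What to change.** Amend section 10.3 before the data are seen:

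1. Include in the primary analysis every consenting patient who answered the sleep items, whether or not the aid-use items are answered, and apply the instrument's own scoring rule for missing items.
2. Report by arm the numbers randomised, offered the form and returning it. Give the reason for non-return where it can be recorded consistently with the consent terms in sections 6.2 and 7.2.
3. Pre-specify a tipping-point analysis of the primary result that varies the non-returner mean separately by arm. Fix in advance the range judged plausible, for example within 0.5 SD of returners, and call the result robust only if the conclusion holds throughout that range.

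The range has to be fixed because the corners matter. At 80% and 70% return, opposite 0.5 SD shifts move the estimate by 0.20 × 0.5 + 0.30 × 0.5 = 0.25 SD. The analysis needs only returned scores and counts by arm, so it uses no sleep data from patients who refused.

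The cost is a few sentences, a return-status and reason field that the section 7.6 extraction list lacks, and one extra analysis. Counts should be taken before the ID log is destroyed under section 11.2. The downside is that either a positive or a null result may have to be reported as less certain.

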#### Risks to participants

1) Allergies: Risk of patient or staff having an allergic reaction to the product.

Likelihood: 1/5 Remote Severity: 4/5 Severe Total risk score: 4/25 low risk Mitigate risk by choosing earplugs and eye masks made from hypoallergenic materials, manufactured in quality plant approved with the CE mark. Earplugs and eye masks themselves or the literature provided with them will describe their composition/materials and they will only be provided to patients with the mental capacity to use them safely in an informed manner (similar to use on an aircraft).

- Swallow/Choking risk: Risk of patients swallowing, breathing in and/or choking on earplugs. Likelihood: 1/5 Unlikely Severity: 4/5 Moderate risk Total risk score: 4/25 low risk Mitigate risk by restricting earplugs and eye masks to patient over 18 years old with capacity and awareness/ability to learning from information leaflets of how to use ear plugs/eye masks.
- 3) Infection risk: Risk of spreading infections from one patient to another and of increasing risk of patients getting otitis externa (outer ear infections). Likelihood: 3/5 Possible
   Severity: 2/5 minor
   Total risk score: 6/25 Low risk
   Mitigate risk by advising patients with ear infections not to use earplugs. Have earplugs and eye masks as single patient use (for disposal on discharge) and replace earplugs and eye masks if soiled or contaminated.
- Pressure sores: Risk of earplugs and eye masks causing a pressure ulcer if left in the bed. Likelihood: 1/5 Remote Severity: 3/5 moderate Total risk score: 3/25 Low risk Mitigate risks by good nursing practice of checking the bed for anything lost on top of the mattress, making the bed daily and frequently turning patients with high risk of pressure ulcers, as well as pressure reducing mattresses and pressure removal from damaged sites.
- 5) Increased confusion/risk of falls: increased confusion as patients forget to remove ear plugs and or eye masks and attempt to walk with ear plugs/eye masks still in place. NB/There is no evidence that this occurs, but it is conceivable that it could. Likelihood: 2/5 unlikely Severity: 3/5 moderate Total risk score: 6/25 Low risk Mitigate risk by never applying earplugs and eye masks to a patient without their express and informed request. Removing/not supplying ear plugs/eye masks to confused/confused patients who do not have mental capacity to use the aids.

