#### 7.7. Discontinuation/Withdrawal of Participants from Study

Each participant has the right to withdraw from the study at any time. In addition, the Investigator may discontinue a participant from the study at any time if the Investigator considers it necessary for any reason including:

- Ineligibility (either arising during the study or retrospectively having been overlooked at screening)
- Withdrawal of Consent
- Allergy/ adverse event from intervention

If a patient withdraws, or is withdrawn, the reason will be recorded. If a patient dies during the admission, this will be recorded and the certified primary cause noted.

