#### 9. SAFETY REPORTING

### 9.1. Definition of Serious Adverse Events

Clinical Research Protocol Template version 10.0 CONFIDENTIAL © Copyright: The University of Oxford and Oxford University Hospitals NHS Foundation Trust 2015 Page 10 of 15 A serious adverse event is any untoward medical occurrence that:

- results in death
- is life-threatening
- requires inpatient hospitalisation or prolongation of existing hospitalisation
- results in persistent or significant disability/incapacity
- consists of a congenital anomaly or birth defect.

Other 'important medical events' may also be considered serious if they jeopardise the participant or require an intervention to prevent one of the above consequences.

NOTE: The term "life-threatening" in the definition of "serious" refers to an event in which the participant was at risk of death at the time of the event; it does not refer to an event which hypothetically might have caused death if it were more severe.

It is anticipated that patients will experience many events. With the exception of falls and deaths these will **not** be recorded because the likelihood of the intervention causing serious harm is considered very small, and collecting the data would be excessively burdensome and unjustified.

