#### 9.2. Reporting Procedures for Serious Adverse Events

A serious adverse event (SAE) occurring to a participant should be reported to the REC that gave a favourable opinion of the study where in the opinion of the Chief Investigator the event was 'related' (resulted from administration of any of the research procedures) and 'unexpected' in relation to those procedures. Reports of related and unexpected SAEs should be submitted within 15 working days of the Chief Investigator becoming aware of the event, using the HRA report of serious adverse event form (see HRA website).

All SAEs (other than those defined in the protocol as not requiring reporting) must be reported on the Oxford University Hospitals NHS Trust SAE reporting form to OUH study team within 24 hours of the Site Study Team becoming aware of the event by email or fax.

In the unlikely event that a Serious Adverse Event is identified, it will be reported to the R&D office immediately. SAE reports should be faxed or emailed to: [name] or [contact]

All SAE information must be recorded on an SAE form and faxed, or scanned and emailed, to R&D. Additional and further requested information (follow-up or corrections to the original case) will be detailed on a new SAE Report Form and faxed/emailed to R&D.

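### Patients who leave because of a reaction to the aids and have no questionnaire may be missed by the only aid-specific harm summary

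*Combined protocol and SAP*

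**What the plan says.** Section 10.3 has a single rule for who is analysed: "All participant data will be used excluding those that withdrew consent or did not complete the study questionnaire". No separate safety set is defined.

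Section 10.1 lists, as a secondary analysis, "Reported use of and problems with the earplugs and eye masks". It gives no denominator or data source.

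Section 7.7 lists reasons for which the investigator may discontinue a participant from the study. One is "Allergy/ adverse event from intervention"; withdrawal of consent is listed separately. It adds: "If a patient withdraws, or is withdrawn, the reason will be recorded".

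The risk list in section 3 opens with "Allergies: Risk of patient or staff having an allergic reaction to the product" and also names ear infection and falls.

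On other events, section 9.1 says "With the exception of falls and deaths these will not be recorded". Section 9.2 sends serious adverse events to the R&D office and, where related and unexpected, to the ethics committee: "Reports of related and unexpected SAEs should be submitted within 15 working days".

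Sections 4, 5 and 7.6 place the one questionnaire more than one day after recruitment. The section 7.6 list of items extracted after discharge covers demographics, dates, length of stay, falls and zopiclone doses. It does not include the reason for withdrawal.

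**The concern.** The rule in 10.3 is triggered by having no form, and a reaction to the aids is one way of coming to have no form. Where that happens, the exclusion removes the event that the problem summary is meant to count, and the patient leaves both numerator and denominator.

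At stake is the trial's statement on how well the aids are tolerated. A report of few or no problems among completers could stand beside several recorded withdrawals for allergy or other reactions that appear nowhere in the results. This point concerns the harm summary only, not the sleep comparison.

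**Working it through.** **No figure to reproduce.** The plan states no problem rate, withdrawal rate or completion rate. Section 10.2 says there are no data on loss of patients and sets 400 by feasibility. With equal-chance allocation (section 7.4), about 400/2 = 200 patients are expected to receive the aids. All other inputs below are assumptions.

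**Tracing one patient through the text**
1. The patient receives the aids at recruitment (7.4) and can use them before the form is due (5, 7.6).
2. The patient is discontinued for a reaction and the reason is recorded (7.7).
3. If no form is completed, 10.3 excludes the patient.
4. The recorded reason is not in the 7.6 extraction list and is in no analysis in 10.1.
5. Section 9.1 does not collect the event separately unless it is a fall or a death. Section 9.2 handles it only if serious, and for safety reporting rather than the trial results.

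**Direction.** Let c be completers given the aids who report a problem, n the completers given the aids, and w those withdrawn for a reaction before the form.

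- Rate under 10.3: c/n
- Rate with reaction withdrawals counted: (c + w)/(n + w)
- Difference: w(n − c)/[n(n + w)]

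The difference is never negative, and it is zero when w = 0.

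**Size under assumed values.** Let m = 40 patients lack a form for other reasons, so n = 200 − 40 − w = 160 − w and n + w = 160.

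| c | w | n | c/n | (c + w)/160 |
|---|---|---|---|---|
| 0 | 0 | 160 | 0% | 0% |
| 0 | 2 | 158 | 0% | 1.25% |
| 0 | 5 | 155 | 0% | 3.13% |
| 0 | 10 | 150 | 0% | 6.25% |
| 5 | 0 | 160 | 3.13% | 3.13% |
| 5 | 2 | 158 | 3.16% | 4.38% |
| 5 | 5 | 155 | 3.23% | 6.25% |
| 5 | 10 | 150 | 3.33% | 9.38% |

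Check of one row against the formula: c = 5, n = 155, w = 5 gives 5 × 150/(155 × 160) = 3.02 points, which equals 6.25 − 3.23.

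With m = 0 and c = 10, w = 1 gives 10/199 = 5.03% against 11/200 = 5.50%, and w = 10 gives 10/190 = 5.26% against 20/200 = 10.00%. The shortfall is about 0.5 to 4.7 points.

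**A report of zero problems.** The exact two-sided 95% upper limit for 0/n is 1 − 0.025^(1/n): 2.31% for n = 158, 2.35% for n = 155 and 2.43% for n = 150. At w = 2 the rate with withdrawals counted (1.25%) is inside that limit. At w = 5 (3.13%) and w = 10 (6.25%) it is above it.

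**Choice of denominator.** Dividing by all 200 would treat the 40 patients without a form as problem-free. With c = 5 and w = 0 that moves 5/160 = 3.1% down to 5/200 = 2.5%, which is a new downward bias. The combined rate should use n + w.

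**The case against.** The strongest reply is that the loss needs a chain the documents do not establish: a reaction, then leaving the study, then no form. Section 10.3 excludes withdrawn consent or a missing questionnaire, not discontinuation by the investigator as such. Section 5 gives the form to all patients, and nothing bars a discontinued patient from completing it. Use of the aids is the patient's choice, so someone with a reaction can stop using them, stay in the study and report the problem. This stands. A reader might infer that the worst reactions never reach the reported rate. The documents do not support that, nor do they say that the worst reactions lead to withdrawal.

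A reader might also infer that this is the only look at harm in the plan. It is not. Falls are a named risk of the aids and are compared between arms with two-tailed tests, though listed under the expectation "Less falls over their hospital stay". Deaths are recorded, and serious events are reported. But a falls comparison cannot show allergy or ear infection, and it is subject to the same 10.3 exclusion.

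Nor are the events lost, since 7.7 captures the reason. What is missing is a plan to tabulate it.

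The scope of 10.3 can be disputed: its heading refers to outcome measures, and aid problems are in neither outcome table. The questionnaire is not in the documents, so its problem item cannot be checked. Yet the sentence covers all participant data, and no other analysis set is given.

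Finally, the risk list rates allergy as remote (1/5), so w = 5 or 10 may be pessimistic for allergy alone. That limits the likely size but does not alter the rule.

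**Conclusion.** The point holds in a limited form. As written, 10.3 can remove from the only aid-specific harm summary a patient given the aids who leaves because of a reaction and has no form. The reason recorded under 7.7 enters no planned analysis that would bring the patient back. Compared with a rate that counts reaction withdrawals, the reported rate can then only be too low.

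The size cannot be derived from the documents. In the assumed scenarios with 2 to 10 such withdrawals, 40 other patients without a form and 5 completers reporting a problem, the shortfall is about 1.2 to 6.0 percentage points. It is zero if nobody leaves for a reaction before the form. The conclusion assumes that at least some such patients have no form, and that the problem summary is drawn from the questionnaire.

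**What to change.** - **10.3:** exempt the aid-problem summary from the questionnaire-completion rule.
- **7.6:** add the reason recorded under 7.7 as one column in the spreadsheet.
- **10.1:** report side by side (a) problems reported on the questionnaire, out of completers given the aids; (b) the number withdrawn for an allergy or adverse event from the intervention, out of all patients given the aids; and (c) the number given the aids who have neither a form nor such a reason.
- **If one combined rate is shown:** use (c + w)/(n + w), and do not count patients without a form as problem-free.
- **Where consent for data use was withdrawn:** use only aggregate counts of reasons, as far as the consent terms allow.

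The cost is a few sentences and one column; the reasons are already recorded, so no new assessment is needed. The reported rate may be slightly less favourable. Consent needs care: section 7.2 treats a blank form as refusal for that data, and section 6.2 says data will not be collected from people unable to consent when the form is given. The information sheet may need a line saying that reasons for withdrawal are counted, possibly through an amendment under section 13.3.
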